**D.5. Remote study procedures.** Study assessments and group therapy sessions will be conducted using an encrypted HIPAA-compliant version of Zoom videoconferencing software which we are currently using in several NIH-funded clinical trials during the stay-at-home orders. Informed consent will be collected using an electronic consent form that participants will be asked to complete during the appointment after reviewing the consent form jointly with a staff member.

**D.6. Assessments.** Assessments will be conducted by blinded assessors at baseline, mid-treatment (after session 5), post-treatment (after session 10), and at a 3-month follow-up. Our assessment strategy was specifically designed to allow for remote assessment during the COVID-19 pandemic and thus will only include measures that can be completed using videoconferencing or via the participants home computer. In order to maximize assessment completion, we will increase compensation across assessments (\$50, \$75, \$100, \$125).

**D.6.1. Feasibility and Acceptability.** Assessment of feasibility will include % of eligible patients enrolled, attrition, and study retention. We will use a Feedback Questionnaire (FQ) to obtain qualitative acceptability ratings, which will be modified from FQs used in our prior intervention development projects.

**D.6.2. Primary outcomes.** The Eating Disorder Examination is a widely utilized, semi-structured interview for the assessment of eating disorder symptoms. We will use number of binge episodes in the last 28 days and EDE global scores as the primary outcomes. Remission status will also be evaluated at each assessment following the baseline assessment and will be defined as the absence of any binge episodes or compensatory behaviors in the 28 days prior to the assessment point and an EDE global score within 1 standard deviation of the community norm (EDE global <1.74).

**D.6.3. Secondary outcomes.** We chose to use commonly-used and well-validated measures of depression (Beck Depression Inventory-II), substance use (Alcohol, Smoking, and Substance Involvement Screening Test), and quality of life (Quality of Life Inventory) to assess secondary outcome measures.

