## STATISTICAL DESIGN AND POWER

Descriptive statistics and exploratory graphing will be generated for all variables of interest measured at all time points (i.e., baseline, mid-treatment, post-treatment, 3-month follow-ups). Data summaries will be produced both for the combined sample, and separately by treatment condition. Variables will be transformed if necessary using Box-cox power transformation. Baseline characteristics will be compared between treatment conditions using ANOVA (or non-parametric Kruskal Wallis test, as appropriate) for continuous variables and a chi-square test for categorical variables. Key baseline variables that differ by condition will be considered for use as covariates in the analyses described below.

**Primary Aim 1.** To assess feasibility and acceptability, we will use the following benchmarks: (a) recruitment success: enrollment of 60 patients; (b) attrition: retention of >75% of patients through all assessments; (c) study retention: patients attend at least 90% of all treatment groups; (d) satisfaction: patients express high satisfaction with RRT based on feedback questionnaires.

**Primary Aim 2.** To evaluate the effect of each treatment condition on hypothesized targets, we will model the pattern of change in reward response to palatable food, reward response to day-to-day life activities, social isolation, and loneliness separately over time using multilevel models (PROC MIXED in SAS). The first level will model individual participant's score on the relevant target over time with baseline as time 0. At the second level, the individual intercept and slope will be entered as outcomes with treatment condition as a predictor. We will examine each treatment condition separately. The cross-level interaction between time and treatment condition will be used to determine the effect of treatment condition on the pattern of change in the hypothesized targets. Restricted maximum likelihood will be used to estimate model parameters and to test the significance of random effects. Both linear and higher-order time effects will be examined based on model selection criterion such as Akaike Information Criterion (AIC) and Bayesian Information Criterion (BIC). With the fitted multilevel model structure, statistical contrasts will be performed at mid-treatment, post-treatment, and 3-month follow-up.

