**Power analyses.** Using the method described by Raudenbush and implemented with the software Optimal Design, power calculations were made for mixed effects models. A sample size of 154 (77 for each condition) is required for 80% power to detect a medium effect with the significant level of 0.05 and four assessment points, assuming the ratio of the variability of level-1 coefficient to the variability of level-1 residual is one. Fritz and MacKinnon documented sample size requirements to guarantee 80% power at the significance level of 0.05 for mediation models. Under the assumption of a medium effect for intervention with the mediator and a medium effect for the mediator on outcome controlled for intervention, the required sample size is 72 in total with 36 per intervention arm to achieve 80% power in simple mediation models. Given our relatively small sample size ( $n=60$ ), our study is powered to detect large effect sizes. While we observed large effect sizes in our pilot trial of RRT compared to a wait list control, we anticipate that the effect sizes may be smaller in the current trial as supportive therapy is an active treatment condition. It is likely that we may be underpowered for formal tests of statistical significance in this preliminary study. We will rely on effect sizes for interpretation when underpowered.

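### Primary Aim 2 does not say that treatment predicts curvature over time, so whether a plateau or fade can show in the arm difference is left to a low-powered AIC/BIC choice, or is ruled out on a literal reading

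*SAP*

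**What the plan says.** SAP, Statistical Design and Power, Primary Aim 2, fits a two-level growth model to each target, with baseline as time 0. Treatment enters in two statements: "At the second level, the individual intercept and slope will be entered as outcomes with treatment condition as a predictor", and "The cross-level interaction between time and treatment condition will be used to determine the effect of treatment condition on the pattern of change". On the shape of time it says "Both linear and higher-order time effects will be examined based on model selection criterion such as Akaike Information Criterion (AIC"), with BIC named alongside. Estimation is by REML. The visit-specific results come from the selected model: "With the fitted multilevel model structure, statistical contrasts will be performed at mid-treatment, post-treatment, and 3-month follow-up". No polynomial order is named, and no sentence says whether treatment predicts a higher-order term if one is kept.

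Protocol D.6 sets the assessments at "baseline, mid-treatment (after session 5), post-treatment (after session 10), and at a 3-month follow-up". Two follow-up visits therefore fall within or at the end of treatment, and one falls after a long interval without it. The SAP's power paragraph concedes that the trial may be underpowered for formal tests, and says effect sizes will then carry the interpretation.

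**The concern.** Treatment ends at session 10, so a plateau or partial loss by 3 months is a plausible shape for the arm difference, and the follow-up visit is there to show it. A quadratic main effect of time bends both arms equally and leaves the arm difference at intercept plus slope times time. Only a treatment-by-quadratic term, or a more flexible time structure, lets the difference itself bend.

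The visit contrasts are the effect sizes that a pilot of this kind delivers. Protocol A.6 says the trial is to show whether the intervention merits a fully powered test. If the model forces a line, or usually falls back on one, a fading effect can be reported as a growing one and the post-treatment effect is understated.

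**Working it through.** **The plan's own figure.** The SAP states: "A sample size of 154 (77 for each condition) is required for 80% power to detect a medium effect" (alpha 0.05, four assessments, variance ratio 1). With linear-change contrast weights −1.5, −0.5, 0.5, 1.5 (sum of squares 5), the sampling variance of a slope is 1/5 = 0.2. The noncentrality is N·d²/(4 × 1.2). For d = 0.5 and N = 154 this is 154 × 0.25/4.8 = 8.02, which gives power 0.804, so the figure reproduces. At N = 60 the same formula gives 41% for d = 0.5 and 79% for d = 0.8. This agrees with the SAP's statement that only large effects are within reach. It does not settle how treatment enters the model.

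**Inputs for the check.**
- From the documents: 30 per arm (Protocol A.7), four assessments (D.6), weekly sessions (D.2).
- Assumed: follow-up 13 weeks after session 10, so t = 0, 0.5, 1.0, 2.3 in units of 10 weeks. Intercept variance 0.5, residual variance 0.35, slope variance s = 0.03 per (10 weeks)². Effects are in SD units.
- Assumed true arm differences: half-fade 0/0.25/0.50/0.25 and plateau 0/0.25/0.50/0.50. The documents give no variances or effect shapes for these targets.

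**Literal model (arm difference = a + b·t).** With a random intercept, a random slope and independent residuals, generalised least squares on (1, t) gives the ordinary least-squares line. The fitted values therefore do not depend on the assumed variances. Mean t = 0.95 and Sxx = 0.9025 + 0.2025 + 0.0025 + 1.8225 = 2.93.
- Half-fade: mean difference 0.25; Sxy = 0.2375 + 0 + 0.0125 + 0 = 0.25; b = 0.25/2.93 = 0.0853; a = 0.25 − 0.0853 × 0.95 = 0.169. Fitted: 0.17/0.21/0.25/0.37.
- Plateau: mean 0.3125; Sxy = 0.5875; b = 0.2005; a = 0.122. Fitted: 0.12/0.22/0.32/0.58.
- Half-fade with visits coded as equally spaced: 0.10/0.20/0.30/0.40.

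**Precision under the half-fade.**
- The variance of b is (2/30)(0.35/2.93 + 0.03) = 0.00996, so its SE is 0.0998.
- The interaction test has z = 0.0853/0.0998 = 0.85, or about 14% power. The chance that the fitted slope is positive, which puts follow-up above post-treatment, is Φ(0.85) ≈ 80%.
- A simple change-from-baseline contrast at post-treatment has variance 2 × 0.35 + 0.03 = 0.73. Its SE is √(0.73 × 2/30) = 0.221, z = 0.50/0.221 ≈ 2.27, power 62%.
- The fitted post-treatment contrast has SE √[(2/30)(0.5 + 0.03 + 0.35(0.25 + 0.05²/2.93))] = 0.203 and bias of about −0.25. Coverage of its 95% interval is about 77%.
- Under the plateau the interaction test has 52% power, against 62% for the change contrast.

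**Kinder model (treatment may enter t²).** A fixed quadratic arm difference is adequate: bias is about 0.05 SD or less at every visit. Selection was simulated among three models: linear time with a linear arm difference, quadratic time with a linear arm difference, and quadratic time with a quadratic arm difference. The criterion was ML deviance plus 2 or log(60) per parameter, with the covariance treated as known and a common trend of 0/0.3/0.6/0.6.

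| True shape | Quadratic arm term selected, AIC / BIC | Mean fitted post and follow-up, AIC | Mean fitted post and follow-up, BIC |
|---|---|---|---|
| Plateau | 54% / 30% | 0.44, 0.52 | 0.40, 0.54 |
| Half-fade | about 75% / 52% | 0.45, 0.27 | 0.41, 0.29 |

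Under the half-fade, follow-up is ranked above post-treatment in 24% (AIC) or 39% (BIC) of trials.

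**Visit as a factor.** The follow-up minus post-treatment difference between arms has variance (2/30)(0.70 + 0.03 × 1.3²) = 0.0500, so its SE is 0.224. The wrong-order probability is Φ(−0.25/0.224) = Φ(−1.12) ≈ 13%. Root mean squared error at post-treatment under the half-fade is 0.24, against 0.25 (AIC) and 0.27 (BIC). If the effect is truly linear it is 0.24, against about 0.22.

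**The case against.** A reader might infer that the SAP fixes a straight-line treatment effect. The documents do not support that. The same paragraph provides for higher-order time effects, takes the contrasts from the selected structure, and never excludes treatment from the added terms. The intercept-and-slope sentence comes before the higher-order provision and can be read as describing the base model. The stated purpose is the effect on the pattern of change, and a further sentence says each condition will be examined on its own, which might mean arm-specific curves. All of this stands.

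A reader might also infer that a fading effect would necessarily be misreported. That too goes further than the text. The SAP plans descriptive summaries and graphs at every time point by condition, so observed means would sit beside the model.

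The size depends on assumptions. With effects of 0.80 SD and somewhat different variances, the quadratic arm term is selected in 92% (AIC) or 77% (BIC) of half-fade trials. In the 0.50 SD half-fade, the literal model's coverage is poor at post-treatment but 95% at mid-treatment and 93% at follow-up. Under a plateau with no slope variance, interaction power is 61% against 64%, almost no loss. The change contrast is also favoured by being placed at the assumed peak of the effect.

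What the objection does not remove is the silence about treatment on higher-order terms, or the dependence on selection. The SAP itself expects effects smaller than the large ones in its earlier pilot. At 0.50 SD the criteria miss the half-fade in about 25% (AIC) or 48% (BIC) of trials.

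**Conclusion.** The concern holds as an under-specified model that should be changed. The SAP names treatment as a predictor of intercept and slope only, and leaves curvature in the arm difference unstated. An analyst could follow the text and fit a line that turns 0.50 then 0.25 into 0.25 then 0.37. That distortion rests only on the assumed visit times and effect shape. An analyst who takes the kinder reading avoids most of the bias when the quadratic arm term is chosen, but at 30 per arm it often is not. The wrong ordering then arises in 24% or 39% of half-fade trials, against 13% with visit as a factor. These percentages also rest on the assumed variances, a 0.50 SD peak effect and a known covariance.

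It is tempting to add that target engagement must be decided on the post-treatment contrast alone. That would be a choice of decision rule; the documents do not require it, and it is not part of this point.

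**What to change.** In Primary Aim 2, model visit as a four-level factor with an arm-by-visit interaction, and take the planned mid-treatment, post-treatment and 3-month contrasts from that model. If a growth curve is preferred, state that treatment predicts every time term, or use two linear pieces with a knot at post-treatment. In either case, fix the form in advance and do not select it by AIC/BIC. Use actual assessment times in any growth curve.

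The cost is a few sentences of SAP text and two more fixed-effect parameters for the arm difference per target (four visit differences in place of an intercept and a slope). Intervals are slightly wider if the true effect is linear: root mean squared error at post-treatment is 0.24 against about 0.22 under the assumptions above. No change to visits, measures or sample size is needed.

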## **A.7. Current study and specific aims.**

In the current study, we will revise our existing 10-session group RRT treatment manual to specifically address the challenges in building social support and enhancing both momentary and sustained reward during the COVID-19 pandemic (Preliminary Aim 1). In months 2-18, we will conduct a small pilot RCT that will randomize individuals to receive either 10-sessions of RRT (n=30) or supportive therapy (n=30), both delivered as group-treatments via videoconferencing software. The specific aims of the current study are to confirm the feasibility and acceptability of RRT for EDs (Primary Aim 1), evaluate the ability of RRT to engage critical targets including reward to day-to-day life activities, reward to palatable foods, social isolation, and loneliness (Primary Aim 2), and provide preliminary estimates of efficacy in reducing ED symptoms at both post-treatment and a 3-month follow-up (Primary Aim 3). We will also evaluate the impact of RRT on secondary outcome variables including depression, substance use, and quality of life (Secondary Aim 1).

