**Primary Aim 3.** Analyses will be conducted via linear mixed effects models for longitudinal data, which increase power by fully exploiting the strong correlation in treatment outcomes of interests (i.e., percent binge frequency reduction and percent change in EDE global eating pathology) across time. Patterned covariance matrices as implemented in (PROC MIXED in SAS) and will be used to evaluate between group differences for percent binge reduction and percent change in EDE global eating pathology across the study as a whole, and at each assessment post-baseline. Separate variance components will be used to capture therapist and participant-within-therapist variation. The within-subject covariance matrix will be assumed common across study arms, with an exponential variance function to deal with heteroscedasticity and a continuous-time AR(1) correlation matrix to accommodate residual autocorrelation over the unequal-size time intervals between follow-ups. Outcomes at all four time points will be estimated jointly for maximum statistical efficiency in the presence of intermittent missingness and loss to follow-up. The model will include random effects for subject and time (with higher-order effects if needed to capture nonlinear change), and fixed effects for treatment arm, time by treatment interaction, demographic information, and baseline values of binge frequency and global eating pathology. Time-specific covariate-adjusted contrasts will be used to compare outcome between groups.

**Secondary Aim 1.** We will use the same analytic approach described above for Primary Aim 3 but will test the impact of treatment condition on secondary outcomes including depression, substance abuse, and quality of

life.

**Attrition.** Patterns of missing data will be examined. Likelihood-based estimation methods and multiple imputation models will be used to handle missing data. In addition, we will use Hedeker and Gibbons' procedure to examine if dropouts influence the multilevel model results. If the missingness mechanism is related to the missing outcome itself, we will use sensitivity analyses to explore how robust our findings are with respect to a range of assumptions regarding missing data.

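### Primary Aim 2 estimates a baseline difference between arms that randomisation makes zero in expectation; a common baseline mean would give more precise target-engagement contrasts at no cost

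*SAP*

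**What the plan says.** All SAP references are to the section Statistical Design and Power.

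- **Primary Aim 2, level 1.** The model is for the "individual participant's score on the relevant target over time with baseline as time 0", so the intercept is the baseline mean and the baseline score is part of the outcome vector.
- **Primary Aim 2, level 2.** "the individual intercept and slope will be entered as outcomes with treatment condition as a predictor".
- **Declared test.** "The cross-level interaction between time and treatment condition will be used to determine the effect of treatment condition" on the pattern of change.
- **Visit contrasts.** From the same fitted model, "statistical contrasts will be performed at mid-treatment, post-treatment, and 3-month follow-up". The SAP does not say whether these compare levels or changes from baseline.
- **Covariates.** The one rule that could reach Aim 2 is in the opening paragraph: "Key baseline variables that differ by condition will be considered for use as covariates in the analyses described below".
- **Primary Aim 3, for comparison.** The fixed effects there include "baseline values of binge frequency and global eating pathology", so that aim prespecifies baseline adjustment for its own outcomes.

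Protocol section A.7 gives the design: 60 participants, randomised 30 to each arm.

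**The concern.** Baseline precedes treatment. In a randomised trial the expected arm difference at time 0 is zero, so estimating it spends information on a quantity already known. In this model the fitted arm difference in level at a later time t is the intercept difference plus t times the slope difference, and a chance gap at baseline feeds into it.

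The general covariate rule does not repair this. It is discretionary, is triggered by observed differences, and does not name the target's own baseline score, which in this model is already the time-0 outcome.

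Target engagement is a primary aim. The SAP's power paragraph accepts that formal tests may be underpowered and says that effect sizes will then carry the interpretation. Point estimates that move with a chance baseline gap, or that are less precise than they could be, therefore matter more here than in a trial that rests on a powered test.

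**Working it through.** **Inputs.** From the documents: 30 per arm (Protocol A.7); significance level 0.05, four assessments, and ratio of slope variance to residual variance of 1 (SAP, Power analyses). Assumed, because the documents do not give them: a medium effect is 0.5; two-sided test; times 0, 1, 2, 3; intercept variance 1 (also 2); intercept-slope correlation 0 (also -0.3 and 0.3); complete data; no clustering by therapist or group.

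**1. The SAP's own figure.** The SAP says "A sample size of 154 (77 for each condition) is required for 80% power to detect a medium effect". For a linear slope difference:
- reliability = 1 / (1 + 1/Σ(t - 1.5)²) = 1 / (1 + 1/5) = 0.833
- noncentrality = N × reliability × δ² / 4 = 154 × 0.833 × 0.25 / 4 = 8.02
- power from F(1, 152) = 80.4%

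So 154 reproduces with equally spaced times. That is the reason for using this coding below.

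**2. Size of a chance baseline gap.** SE = √(2/30) = 0.26 SD; 95% range ±0.51 SD. The probability of an absolute gap above 0.3 SD is about 25%.

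**3. Model as planned.** With variance ratio 1 and zero correlation, the covariance of the (intercept, slope) arm differences is (2/30) × [[1.7, -0.3], [-0.3, 1.2]]. In units of 2/30:
- interaction: 1.2
- level contrast at t: 1.7 - 0.6t + 1.2t², which is 2.3, 5.3 and 10.7 at t = 1, 2, 3

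**4. Common baseline mean.** Setting the intercept difference to zero gives slope variance 1.2 - 0.3²/1.7 = 1.147, and the contrast at t has variance 1.147t².

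| Quantity | Arm in intercept | Common baseline | Reduction |
|---|---|---|---|
| Mid-treatment level contrast | 2.3 | 1.147 | 50% |
| Post-treatment level contrast | 5.3 | 4.588 | 13% |
| Follow-up level contrast | 10.7 | 10.324 | 4% |
| Time-by-arm interaction | 1.2 | 1.147 | 4% |

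At N = 60, power of the interaction test for δ = 0.5 moves from 41% to 43%.

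**5. Without the straight-line assumption.** With unstructured time the reduction in a level contrast is r², the squared correlation with baseline. The implied variances are 2, 3, 6 and 11, and the covariance with baseline is 1 throughout. So r² = 1/6, 1/12 and 1/22, or about 17%, 8% and 5%. In this base case the reductions against change contrasts are the same.

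**6. Carry-over.** In the planned linear model, each unit of chance baseline gap shifts the expected level contrast by 0.70, 0.55 and 0.40 at the three visits. It shifts the slope difference by -0.15 per time step, which is regression to the mean.

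**7. Range.** With intercept variance 1 or 2 and correlation -0.3 to 0.3, at times 0-3:
- interaction: 0-18%
- linear level contrasts: 42-71%, 4-40% and 0-25% at the three visits
- unstructured level contrasts: 10-40%, 2-31% and 0-25%

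Time coding also matters, because a variance ratio of 1 means something different in each time unit. Taking visits at weeks 0, 5, 10 and 23 (assumed) with the base-case variances, the post-treatment and interaction reductions are 33% and 3% if week 23 is rescaled to 3, but 1% and 0.1% with time in raw weeks. The common-baseline model was not less precise in any setting.

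**The case against.** The Aim 2 model is a standard and valid growth model, in a pilot that is open about its limited power. Four objections carry weight.

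- **The declared test is hardly affected.** The time-by-arm interaction nets out the level difference. Its gain is about 4% in the base case and nil in some settings. This stands.
- **The contrasts may not be differences in level.** The SAP leaves this open and also says that each arm will be examined separately. For a change contrast in the linear model the intercept difference cancels, and only the interaction's gain applies. This stands, and is itself a reason to define the contrasts.
- **The large mid-treatment gain owes much to linearity.** With a common intercept and linear time, all three contrasts are one slope difference multiplied by t and share one test statistic. The SAP allows higher-order time terms chosen by AIC or BIC, so the unstructured figures are the safer guide for visit contrasts.
- **Baseline variables that differ may be adjusted for.** This mitigates little, for the reasons given under the concern.

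A reader might go further and infer that the trial gives up a third of its information, so that 60 patients could act like 90 (60 / 0.67). That figure holds only for the post-treatment level contrast, with linear time and week 23 rescaled to 3. On the coding that reproduces 154, the same contrast gives 60 / 0.866, or about 69. A reader might also infer that Aim 2 is biased, or that a baseline gap of one standard error would by itself be read as engagement. The documents support neither: over repeated randomisation the estimator is unbiased, and the declared test responds to a baseline gap only through regression to the mean.

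**Conclusion.** The point holds as a precision improvement of modest and uncertain size. The plan does estimate a baseline arm difference in Aim 2 that the design sets to zero in expectation, and nothing in either document prespecifies adjustment for the target's own baseline. The consequence is conditional error in level contrasts and some lost precision.

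The visit contrasts are where the gain lies: roughly 5-17% of variance with unstructured time in the base case, and more at mid-treatment if time is linear. These figures rest on assumed intercept variance, correlation, time coding and complete data. Only the direction was common to every setting tried. A common baseline mean also assumes that baseline is measured before randomisation, which the documents imply but do not state.

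**What to change.** In the Primary Aim 2 text of the SAP:

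1. Remove treatment condition from the intercept equation, so that both arms share one baseline mean, and keep the arm-by-time terms.
2. Take the mid-treatment, post-treatment and follow-up contrasts from that model. Say that each is the arm difference at that visit given a common baseline, and say what happens if higher-order time terms are selected.
3. State that the baseline assessment precedes randomisation.

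A similar but not identical alternative is to model the post-baseline visits only, with arm, arm-by-time and the target's baseline score as a prespecified covariate. This would bring Aim 2 closer to Aim 3, which prespecifies baseline values of its own outcomes. It takes time 0 out of the outcome vector, leaves three visits for the growth terms, and loses participants who have no post-baseline score.

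The first option deletes one model term. Neither option needs new data, visits or participants.
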